**Vanderbilt University Medical Center**

## Introduction

Recently, there is a growing interest in the relation between intraoperative hypotension (IOH) and the occurrence of various postoperative adverse events. An increasing number of studies show an association between IOH and outcomes such as mortality, acute kidney injury and myocardial infarction. However, this does not mean that we now understand ‘how low we can go’. For example, heterogeneity in IOH definitions, outcome definitions and study populations makes it difficult to draw firm conclusions about the exact IOH threshold. Nonetheless, the observational nature of the data may be the biggest problem, as residual confounding is still likely to be of great influence.

The main cause of the residual confounding in observational IOH studies may be the current behavior of anesthesia providers. Blood pressure management is a vital part of anesthesia practice, and patients undergoing anesthesia are frequently – if not constantly – being treated for low blood pressures by anesthesia providers. However, blood pressure management is not a one-size-fits-all solution as each patient requires interventions that are tailored his or her needs. This complexity of blood pressure management is very difficult to adjust for during the analysis of IOH. It is very well possible that IOH is merely related to adverse events because it is a symptom of underlying disease severity and comorbidity, rather than being a proof for organ hypoperfusion despite current blood pressure treatment by anesthesia providers. It is thus of

great importance that we improve our understanding of our current circulatory management.

In current clinical practice IOH is quite common. Few anesthesia providers would consider a mean arterial pressure (MAP) below 60 mmHg\* to be clinically acceptable for patients undergoing noncardiac surgery. Nonetheless, up to 50% of patients have a MAP below 60 mmHg at any time point during their surgical procedure, adding up to ten minutes or more during the procedure in 15-25% of all patients. In view of recent scientific evidence, it thus seems imperative that anesthesia providers adhere more strictly to their own clinically acceptable blood pressure thresholds.

Clinical decision support may help anesthesia providers to adhere more strictly to their own clinically acceptable blood pressure thresholds. An automated notification system may alert the anesthesia providers when the blood pressure of their patient drops below 60 mmHg MAP. A recent randomized trial didn't demonstrate any change in blood pressure management as a result of automated blood pressure notifications. Because of the study design, the authors do not provide a satisfactory explanation of why it didn't change blood pressure management. Although randomization at the patient level may seem the appropriate thing to do, there is a serious risk of contamination. When on a given day an anesthesia provider received notifications for the first patient, is it likely that the provider will be more aware of the blood pressure threshold during a next case, even when the subsequent patient was randomized to the control group. The contamination could be one explanation for a 'null-result' for the study. Another explanation would be that the authors did not provide sufficient context to the notifications, which has been suggested to be a requirement for the successful implementation of decision support. The recent randomization trial thus by no means provides sufficient scientific evidence that clinical decision support for IOH does not work.

The current study proposal aims to implement a clinical decision support system for IOH that provides both automated notifications and contextual information. The decision support aims to educate anesthesia providers about the risks that are associated with IOH. Their response to that decision support will allow us to study blood pressure management by anesthesia provid-

---

\* a MAP of 60 mmHg corresponds with a blood pressure of systolic 80 over diastolic 50 mmHg

ers, the effect of decision support on that blood pressure management, and the subsequent impact on postoperative adverse events.

## Overall research question

Does a more strict treatment of intraoperative hypotension (IOH) encouraged through a clinical decision support system (CDSS) reduce postoperative morbidity and mortality in comparison to care-as-usual?

## Specific clinical research questions

*Does a lower incidence of IOH reduce postoperative morbidity and mortality?*

Assuming that the CDSS resulted in a lower incidence of IOH, the postoperative morbidity and mortality will be compared between the intervention group and the care-as-usual group

*How does this relation depend on the anesthetic depth?*

Differences in the administration of intraoperative anesthetics and analgesics between the study groups will be determined. Postoperative morbidity and mortality will then be studied conditional on these differences between study groups.

*How does this relation depend on other treatment choices?*

Differences in the administration of intraoperative vasopressors and inotropes will be compared between study groups. Study groups will also be compared for the differences in total amount of administered intravenous fluids and blood products.

*How does this relation depend on intraoperative conditions and patient comorbidity?*

The relation between treatment, IOH, and postoperative morbidity and mortality may be studied conditional on other vital signs, blood loss, and various patient comorbidity.

## Specific decision making questions

*Does a CDSS for IOH result in a lower incidence of IOH?*

The incidence of IOH will be compared between study groups, overall and conditional on CDSS activity.

*Does a near real-time notification have a greater impact than feedback on performance?*

In this study two types of decision support will be compared. One type consists of near real-time notifications that alerts anesthesia providers when the blood pressure drops below a particular threshold. The second type is an email system that provides feedback on what has happened during the anesthetic case and about the possible consequences.

*What is the role of teamwork in anesthesia management?*

Because the first elements concentrate on the attending anesthesiologist and the latter elements on the in-room providers, this study will provide insight in the anesthesia teamwork. This will be explored by comparing the results according to different roles (e.g. attendings, residents, CRNA, SRNA), years of experience and anesthesia service (multispecialty anesthesia, neuroanesthesia, etc.).

*How does the 'directiveness' of the CDSS influence decision making.*

The staged elements increase in their degree to which they draw the attention of the attending anesthesiologists and in-room provider to the problem of IOH. Nevertheless, only the last phase provides an actionable recommendation and is thus truly directive.

*How does this relation depend on the anesthetic depth?*

Differences in the administration of intraoperative anesthetics and analgesics between the study groups will be determined. The incidence of IOH will then be studied conditional on these differences between study groups.

*How does this relation depend on other treatment choices?*

Differences in the administration of intraoperative vasopressors and inotropes will be compared

between study groups. Study groups will also be compared for the differences in total amount of administered intravenous fluids and blood products.

*How does this relation depend on intraoperative conditions and patient comorbidity?*

The relation between treatment and IOH may be studied conditional on other vital signs, blood loss, and various patient comorbidity.

*What is the effect of risk education?*

The calibration/simulation will not only help to study decisions, but may also train the providers.

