#### *Study design*

[figure not shown]
A single center, interrupted time series study with a nested cluster-randomized trial, randomized at the level of the anesthesia provider (see Figure 1). The study will be performed at Vanderbilt University Medical Center (VUMC). The study will use a 36-month historic cohort of procedures (retrospective data) from the baseline 'off' period, further referred to as the prein-

tervention period. Subsequently, the decision support system is implemented and its effects are recorded during the intervention period using routine clinical data. The decision support system consists of four interventional elements (see paragraph 'Decision support elements'), of which two are aimed at the attending anesthesiologist and two are aimed at the in-room anesthesia provider (the anesthesiology resident, the certified or student nurse anesthetists (CRNA or SRNA)).

The intervention period starts with the nested cluster-randomized trial. At the start of the intervention period, the attending anesthesiologists will be randomized to either of the two elements aimed at the attending. One month later, the in-room providers will be randomized to either of the elements that are aimed at them. The randomization status of the attending anesthesiologists will be maintained. After the third month, all elements will be activated for all users within that user group. This ends the period of the nested cluster-randomized trial. After the fourth month, an add-on for one of the decision support elements will be implemented. The exact nature of this add-on modification is discussed in the section 'Decision support elements'. The entire implementation phase will thus be completed in five months.

The study will then continue to monitor the incidence of the primary end point to reach the estimated sample size. The primary outcome is a routinely collected outcome variable, which enables us to: 1) use a historic cohort as a baseline 'off' period; 2) study the CDSS implementation in a pragmatic setting; and 3) conduct the study in a more cost-effective way. The total intervention period will be 9 months for the VUMC (Figure 1).

Figure 1 - Study design

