### *Decision support elements*

The decision support system consists of four elements that aim to notify anesthesia providers of

the risks of organ injury due to organ ischemia when a patient suffers from IOH. The four elements will be implemented during different stages of the nested cluster-randomized trial period. At the end of the trial period all elements will be simultaneously activated (Figure 1).

The decision support system will be custom designed. The VUMC will implement two elements that provide near real-time notifications into GasChart, its anesthesia information management system (AIMS). The two other interventions consist of feedback emails, which be implemented into the email notification system of the Perioperative Data Warehouse (PDW).

One element of each decision support type will be available for each user group. In other words, a near real-time notification system and a feedback email system will be available for the attending anesthesiologists as well as for the in-room providers. During the cluster-randomized trial period, the near real-time elements will only be activated for a specific case when the anesthesia providers were randomized to near real-time decision support within their user group, as registered in the anesthesia information management system.

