### *Triggers of near real-time notifications*

The near real-time notifications systems will be triggered by a MAP below 60 mmHg (Figure 2). The decision support system will then provide a notification of the AKI risk at VUMC. Depending on how much time the MAP of an individual patient was below a particular threshold, the notification will display the risk of organ ischemia for that patient (mild, moderate or high, see Table 2). An example in time is shown in Figure 2 – examples 1 and 2.

The near real-time notifications for the in-room providers will be continuously displayed within the AIMS. The near real-time notifications for the anesthesiologists will be sent to their pagers. The pager notifications will repeat with a 10-minute interval. Within a single episode of IOH there will be a maximum of four notifications the paging system (Figure 2 – example 3). An episode of IOH is defined as the time that a patient’s MAP drops below 60 mmHg and the first time it reaches a MAP of 60 or higher. When blood pressure has not returned to normal after the four notifications – i.e. after 40 minutes – it is assumed that there is a reason for not increasing the blood pressure. In that instance either the MAP is considered to be appropriate for that patient or the interventions are not sufficiently effective. This prevents anesthesiologists to keep getting notifications throughout the procedure. Even when a new duration threshold is reached, the system will not provide a new notification if four notifications within that episode have already occurred. However, when the blood pressure normalizes for more than 20 minutes, a subsequent IOH episode will again provide notifications to the low MAP. Any risk that is presented, is based on all the previous low MAP values and durations that occurred during the case (Figure 2 – example 4).

Figure 2 - Triggers of near real-time notifications

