### *Secondary end points: patient level*

- 30-day mortality
  - combination of in-hospital mortality and ‘alive-index’ (which checks for visits to the hospital in the electronic healthcare record as indication of being alive)
- In-hospital mortality

- length of hospital stay
- ICU admission
- length of ICU stay (if any)
- readmissions
- AKI stage 2 or greater (to a 200% or more increase in baseline creatinine value)
- postoperative rise in creatinine levels

*Secondary end points: process level*

- the incidence of IOH
- the depth and duration of IOH
- estimated blood loss
- time to discharge readiness at the PACU

*Secondary end points: behavior level*

- anesthetic/analgesic drug use
  - average concentrations of inhalational anesthesia during MAP < 65 mmHg episodes
- average use of the following blood pressure interventions during the entire case
  - vasopressor use
  - inotropic use
  - intravenous fluid administration
  - blood products administration
- time to first blood pressure intervention after MAP drops below
  - 65 mmHg
  - 60 mmHg
  - 55 mmHg
  - 50 mmHg

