## Data collection

Primary and secondary patient end point data are routine clinical data that will be collected from the medical records of the hospital electronic patient record keeping system, which are already linked to the existing perioperative data warehouses. Behavioral end point data will be extracted from the perioperative data warehouse (PDW) of the VUMC. Collection of end point data will automatically be performed, guaranteeing an end point assessment that is independent of the randomization status of providers and procedures.

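### Recorded IOH duration can fall because alerted providers re-read the pressure sooner, and the plan has no rule to separate that from better blood pressure

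*Combined protocol and SAP*

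**What the plan says.** Under Specific decision making questions, the plan asks whether the decision support lowers IOH and answers that "The incidence of IOH will be compared between study groups, overall and conditional on CDSS activity". The process-level list under End points contains the incidence of IOH and, separately, "the depth and duration of IOH". Incidence is not defined. Table 2 grades IOH by total minutes below a threshold, and the sample size section uses MAP below 60 mmHg for 10 minutes.

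The alert works on recorded MAP. Under Triggers of near real-time notifications, "The near real-time notifications systems will be triggered by a MAP below 60 mmHg". The risk shown varies "Depending on how much time the MAP of an individual patient was below a particular threshold". An episode runs from when "MAP drops below 60 mmHg and the first time it reaches a MAP of 60 or higher".

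On data, Study design says of the decision support that "its effects are recorded during the intervention period using routine clinical data". Data collection describes automatic capture as "guaranteeing an end point assessment that is independent of the randomization status of providers and procedures". That section names sources for patient and behavior end points but none for process end points. Process end points are analyzed with segmented regression with random effects.

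The documents give no reading interval, cuff or arterial-line distinction, artifact rule, carry-forward or interpolation rule, or term for measurement frequency.

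**The concern.** Automatic capture means that nobody who knows the allocation decides what is extracted. It does not fix how often pressure is read, and in a patient on intermittent cuff readings that is in the hands of the provider who gets the alert. A natural response to a low-pressure alert is to repeat the reading at once. The low value then stands for a minute or so before it is replaced, while normal values still stand for a full cuff cycle. Recorded time below threshold shrinks on one side only. The historic phase has no alert to cause this.

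Two comparisons are exposed: IOH duration between phases, and real-time notification against feedback email in the nested trial. Emails arrive after the case, so the direct route operates only through the real-time elements and would favor them. The first clinical research question is framed on the assumption that the decision support lowered IOH. An artificial fall in minutes could therefore color how an AKI result is explained, for example as evidence that treating IOH does not help.

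**Working it through.** **No figure to reproduce.** The plan states no effect size, sample size or power for IOH. The check is whether the mechanism can produce a difference when true pressure is the same, and how large.

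**Mechanism by hand.** Take a 5-minute cuff cycle with carry-forward scoring. A single low reading followed by a normal scheduled reading counts as 5 minutes below 60. If it is repeated after 1 minute and the repeat is normal, it counts as 1 minute. Four recorded minutes disappear with no change in pressure.

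**Simulation.** All inputs are assumptions, because the documents supply none:
- 20,000 two-hour cases per setting.
- MAP mean 78 mmHg, between-case SD 7, within-case SD 9, autocorrelation time 10 minutes, reading error SD 3.
- Cuff every 3 or 5 minutes.
- Each scheduled reading below 60 is repeated once, 1 minute later, with probability q. The true MAP is the same with and without repeats.

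Fall = 1 − (mean recorded minutes below 60 with repeats) / (mean without repeats).

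| q | 3-min cycle, carry-forward | 5-min cycle, carry-forward | Linear interpolation |
|---|---|---|---|
| 0.25 | 6.3% | 7.6% | about 2% |
| 0.50 | 12.5% | 15.3% | about 4% |
| 0.75 | 19.0% | 22.7% | about 6% |

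- Share with 10 minutes or more below 60 (5-minute cycle, carry-forward): about 29% without repeats, then 27 / 24 / 22%.
- Share with any MAP below 60: 51.0% with and without repeats (3-minute cycle), 44.6% with and without (5-minute cycle). The triggering low reading stays in the record, so this measure cannot fall.

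**Second model.** 4,000 cases of 150 minutes, mean MAP 72, reading error SD 0, 4 or 8, every low reading repeated once. Across 3- and 5-minute cycles, recorded minutes fell 8-41% with carry-forward and 1-18% with interpolation. With minute-by-minute readings the fall was 0%. The share above 10 minutes fell in most 3- and 5-minute settings but not all: at 5 minutes with no reading error it went from 34.4% to 35.6% under carry-forward. The shares with any MAP below 60 and any MAP below 65 were unchanged throughout.

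**What shrinks it** (carry-forward, 5-minute cycle):
- Usual care already repeats half of low readings and alerts raise this to 75%: 1 − (1 − 0.227)/(1 − 0.153) = 1 − 0.773/0.847 = 8.7%.
- 40% of patients have continuous pressure, with similar minutes below 60, and no repeats in usual care: 0.6 × 22.7% = 13.6% at q = 0.75, and 0.6 × 7.6% = 4.6% at q = 0.25.
- Both together: 1 − (0.4 + 0.6 × 0.773)/(0.4 + 0.6 × 0.847) = 1 − 0.864/0.908 = 4.9%.

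**The case against.** The strongest reply is that the plan's question is about incidence, and incidence read as any MAP below 60 does not move. That stands. The point applies only to duration, and to incidence if it is defined by a duration cut. The plan leaves this open.

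Second, the inputs are unseen. The shared MAP stream is an inference, and nothing in the documents shows that alerts prompt re-reading. The size depends heavily on a scoring rule that the plan does not give. That also stands, and is why the result is a range that reaches zero.

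Third, the plan collects vasopressor, fluid and anesthetic use and time to first intervention. Fewer IOH minutes with unchanged treatment would be a warning sign. This helps, but no rule ties those end points to the reading of the IOH result.

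A reader might infer that the artefact would usually reach significance. A simple two-sample test at the planned sizes, with the simulated SD of about 13 minutes, has SE = 13 × √(1/2005 + 1/8019) = 0.325 minutes. The planned analysis is segmented. With 36 and 9 monthly points and level and slope terms, the SE of the level change is about 0.61 to 0.65, roughly double, before clustering. Significance rates from the simple test would overstate the risk, and none is claimed here.

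A reader might also infer that the AKI result is contaminated. AKI is defined by creatinine, compared by phase under intention-to-treat, and not conditional on an observed fall in IOH. The primary analysis set does use recorded MAP below 65, but the share with any such reading did not change in the check.

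**Conclusion.** The concern holds for IOH duration and for any duration-cut definition of IOH incidence. With true pressure unchanged, one prompt repeat of 25-75% of low cuff readings lowers recorded minutes below 60 by about 6-23% under carry-forward and 2-6% under linear interpolation. The fall is zero with minute-by-minute readings. It is toward the low end, or below it, if usual care already repeats low readings or many patients have continuous pressure.

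This rests on three assumptions: the end point uses the same routine readings as the alert, many cases have intermittent cuff readings, and alerts raise the repeat rate. The first is a strong inference. The other two can be checked in data the trial will hold.

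The documents do not support the stronger conclusion that the decision support would appear to work through measurement alone, or that its clinical result is unsafe. The defect is narrower: as written, the plan could not tell fewer minutes of low pressure from more frequent reading. It deserves correction because the correction is cheap.

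**What to change.** In the process-level end point list and the process-level analysis section:

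1. State the MAP source, the artifact rule and the carry-forward or interpolation rule. Apply one scoring rule for IOH duration in both phases and both nested arms. Define IOH incidence, saying whether it carries a duration cut.
2. Pre-specify a sensitivity analysis that thins readings to a common fixed interval, preferably using scheduled automatic readings only and excluding repeats taken soon after a low reading. Taking simply the first reading in each epoch is not neutral: a repeat can fall into the next epoch and become its first reading, which left about +1 to +3% in simulation.
3. Add an analysis restricted to continuous-pressure cases.
4. Report readings per hour and the share with continuous pressure, by phase and nested arm.
5. Attribute a fall in IOH duration to the decision support only if it persists in items 2 and 3.

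The cost is SAP wording and a little extra derivation and analysis on routinely collected data, provided scheduled and repeat readings can be told apart there. The thinned version measures short episodes less precisely, which is why it is proposed as a sensitivity analysis and not as the main derivation.
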